#### 4.2. Duration of study (whole population)

The total duration of the study will be approximately 30 months, including 18 months of active enrollment.

Planned start date (first participant on study): September 2022.

The planned study termination (clinical cutoff) corresponds to the date when each participant has been followed-up for 12 months or is deceased.

End of study occurs when all of the following criteria have been satisfied:

- The trial is closed to enrollment

AND

- The last included participant has been followed for 12 months or if deceased, each participant has been followed-up for 12 months or is deceased.

### 4.3. Definitions of duration of study per participant

Depending on the period (light or dark blue on the figure 2), participants will be included either in the control arm or in the intervention arm.

Participants will be evaluated at scheduled visits as described in section 7.

Each participant will be followed-up for 12 months after inclusion.

If funding permits, a follow-up of patients up to five years after protocol inclusion will be planned. Minimal data will be collected from patient's chart including relapse or progression, survival and institutionalisation.

Participants will be considered to be **on-study** from the signature of the informed consent to the end of follow-up period.

Participants may withdraw their consent at any time; no further study activities will be conducted with them.

**Study discontinuation** occurs when an enrolled participant ceases to participate in the study, regardless of the reason (as detailed under “Follow-up” in Section 7). Participants have the right to withdraw consent at any time; if this is the case, no further follow-up should be performed.

The date and reason for study discontinuation will be clearly documented in the participant’s eCRF.

## 5. Statistical considerations

### 5.1. Hypotheses and number of participant needed

Sample size calculations were drawn in order to be able to detect a mean difference of 10 points or more (on a score from 0 to 100), should the intervention be effective, for at least one of the three targeted health-related quality of life (HRQoL) scores (common standard deviation of 20 points). Each of the three scales will be independently tested. With a 1.6% two-sided type I error and a statistical power of 90%, the minimum number of patients to include is 222. Accounting for a possible 20% dropouts, the total minimum number of patients to be included is 278. Accounting for the effect of the stepped-wedge study design, with an intra-cluster correlation coefficient of 10% and eight centres included, the number of patients to be included is 720 corresponding to 10 patients on average per step and per centre (Table 2.1)

Randomised investigating sites	Number of patients to be included per step on average	Total Nb of patients to be included control arm	Total Nb of patients to be included Intervention arm	Total nb of patients to be included – Per site
Hospital 1	10	10	80	90
Hospital 2	10	20	70	90
Hospital 3	10	30	60	90
Hospital 4	10	40	50	90
Hospital 5	10	50	40	90
Hospital 6	10	60	30	90
Hospital 7	10	70	20	90
Hospital 8	10	80	10	90
Total	80	360	360	720

**Table 1:** Number of patients who will be included in the control and intervention arm for each of the eight investigating sites. 10 patients will be included per step

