## 3. Study endpoints

### 3.1. Primary endpoint

Quality of life assessed by the EORTC QLQ-C30 (version 3.0) questionnaire at 6 months after GerOnTe inclusion.

Three scales of the QLQ-C30 questionnaire are considered as primary endpoints:

- Normalised global health status score of the QLQ-C30 (version 3.0) questionnaire at 6 months after inclusion (score 0-100);
- Normalised score of the physical functioning scale of the QLQ-C30 (version 3.0) questionnaire at 6 months after inclusion (score 0-100);

Normalised score of the emotional functioning scale of the QLQ-C30 (version 3.0) questionnaire at 6 months after inclusion (score 0-100).

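### Testing the three primary scales at a fixed 1.6% each is valid, but Holm's step-down at an overall 5% would be more powerful for the second and third scale with the same 720 patients

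*Protocol*

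**What the plan says.** Section 3.1 (Primary endpoint) gives three endpoints equal standing: "Three scales of the QLQ-C30 questionnaire are considered as primary endpoints". They are global health status, physical functioning and emotional functioning, all at 6 months.

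Section 5.1 sets the testing rule in the sample-size paragraph: "Each of the three scales will be independently tested. With a 1.6% two-sided type I error and a statistical power of 90" per cent, "the minimum number of patients to include is 222". The target is a 10-point difference with a "common standard deviation of 20 points", "for at least one of the three targeted health-related quality of life (HRQoL) scores". The number is then raised to 278 for 20% dropout, and to 720 for the stepped-wedge design with eight centres and an intra-cluster correlation of 10%.

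No step-down or ordering of the three tests is mentioned. Section 5.2.1 (Analysis strategy) gives a 5% type I error for all comparisons and makes no exception for the primary scales. Section 5.2.3 refers to a separate statistical analysis plan, which is not at hand.

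**The concern.** Under a fixed split, a result on one scale changes nothing for the others. Once one scale has been shown at 1.6%, the other two still face 1.6%. An overall 5% does not require this. After one rejection, only two null hypotheses can still be wrongly rejected, so the remaining error can be shared between two tests and then given wholly to one. Holm's procedure does exactly that.

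With three scales listed as primary, a reader of the results will want to know which of them improved. A fixed split can leave a second or third scale unproven when the same data and the same overall error would establish it.

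**Working it through.** **Inputs from section 5.1:** three scales; 1.6% two-sided each; power 90%; difference 10; SD 20; dropout 20%; ICC 0.10; 8 sites; 10 patients per site and step; 720 in total. Table 1 (90 patients per site, 10 per step) implies 9 steps. **Assumption:** the correlation between the three test statistics is not given; 0.5 is used, with a range of 0 to 0.7.

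**1. The plan's own figures.**
- Normal approximation, per arm: 2(z₀.₉₉₂ + z₀.₉₀)² × (20/10)² = 2(2.409 + 1.282)² × 4 ≈ 109, or 218 in total. The t-test version needs 111 per arm = **222**, as stated.
- 222 / 0.80 = 277.5, so **278**, as stated.
- The Hussey–Hughes variance with 10 patients per cell is 5.753. Individual randomisation of 720 gives 4 × 400 / 720 = 2.222. The design effect is 5.753 / 2.222 = 2.589, and 278 × 2.589 = 719.7, so **720**, as stated.

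The stated numbers are therefore consistent with testing each scale at 1.6%.

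**2. Holm rejects at least as much.** Holm compares the smallest p-value with 5%/3 = 1.67%, the next with 5%/2 = 2.5% and the largest with 5%. It stops at the first failure. All three limits exceed 1.6%, so any p-value at or below 1.6% is also rejected by Holm. Holm keeps the family-wise error at or below 5% under any correlation. Neither statement depends on the simulation below.

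**3. Standard error with 20% loss.** With 8 analysed patients per cell, the within-cell variance is 400 × 0.90 / 8 = 45 and the between-site variance is 400 × 0.10 = 40. For 8 sites and 9 steps:

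Var = 8 × 45 × (45 + 9 × 40) / (84 × 45 + 420 × 40) = 145,800 / 20,580 = 7.08, so SE = 2.66 (2.67 used below).

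Power per scale at 1.6% is Φ(10/2.67 − 2.409) = Φ(1.336) ≈ 91%.

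**4. Fixed 1.6% against Holm.** Simulated trivariate normal statistics, SE 2.67, correlation 0.5:

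| True effects (points) | Result | Fixed 1.6% | Holm |
|---|---|---|---|
| 10, 10, 10 | each scale | 91% | 95% |
| 10, 10, 10 | all three | 80% | 90% |
| 10, 10, 10 | at least one | 98.7% | 98.7% |
| 7, 7, 7 | each scale | 58% | 67% |
| 7, 7, 7 | all three | 33% | 51% |
| 10, 7, 5 | second scale | 58% | 67% |
| 10, 7, 5 | third scale | 30% | 43% |

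The effects below 10 points are illustrations and are not in the protocol. No draw was rejected by the fixed rule and not by Holm. Under the global null, Holm's overall error is 4.4%.

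**5. Sensitivity to the correlation.** Setting power per scale at exactly the planned 90%, with 10 points on all three, the chance of showing all three rises as follows:

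| Correlation | Fixed 1.6% | Holm |
|---|---|---|
| 0 | 73.0% | 87.7% |
| 0.3 | 75.8% | 88.5% |
| 0.5 | 78.2% | 89.3% |
| 0.7 | 81.0% | 90.4% |

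**6. What Holm gives up.** If two scales respond by 10 points and the third is truly null, the chance of a false claim on the third rises from 1.6% to about 4.3% at correlation 0.5, and to about 4–5% over the range. This stays within the overall 5%. With 10 points on all three, about 11% of trials would have at least one scale that is significant by Holm while its 98.3% interval includes zero; with 7 points on all three, about 21%.

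**The case against.** The strongest reply is that nothing here is wrong. The split is valid, the sample size reproduces, and the target is an effect on at least one scale, where Holm gains almost nothing. All of that stands. It limits the point to efficiency, and the gain falls on the second and third scale.

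A second reply is that the 1.6% appears only in the sample-size paragraph. One would size a trial at about 5%/3 for a Holm analysis too, and the analysis plan may already name a step-down. This is possible. But 5.1 does say that the scales are tested independently at that level, so the natural reading is a fixed split. An analysis plan that uses Holm would be better supported if the protocol said so.

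A third reply is that 5.2.1 sets 5% for every comparison, so there is no strict split to relax. A reader might go further and infer that the primary family runs an error of up to 3 × 5% = 15%. The protocol does not establish that: 5.1 sets 1.6% specifically for the primary scales, and the general sentence in 5.2.1 does not say that it replaces it. The two sections do need to be reconciled, and the efficiency point holds only if 5.1 governs the primary tests.

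A reader might also infer that Holm costs nothing. That is true of patients and of the overall 5%, but not of the error on a single null scale or of the match between intervals and tests.

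**Conclusion.** The point holds as an efficiency improvement. That Holm is never less powerful than the fixed 1.6% split, at an overall 5%, is a mathematical fact. The size of the gain rests on the assumed correlation of 0.5, the SE of 2.67 and the assumed true effects. With the planned 10 points on all three scales it is about 4 percentage points per scale and 10 for all three; over correlations from 0 to 0.7, with power per scale set at 90%, the gain for all three is about 9 to 15 points.

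It would be wrong to infer that the primary analysis is invalid, that the trial is underpowered for its stated target, or that 720 must change. The fixed split keeps the overall error at or below 4.8%, power for at least one scale is about 98.7% under either rule, and the sample-size chain reproduces. The 0.2% of error left unused is only the rounding of 1.67% to 1.6%; the gain comes from the later Holm steps.

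**What to change.** - **Section 5.1:** state that the three primary scales are tested with Holm's step-down procedure at an overall two-sided 5%: smallest p-value against 1.67%, next against 2.5%, largest against 5%, stopping at the first non-significant result. The 1.6% can stay as the level used for sizing, since the first Holm step is no stricter, and 720 is unchanged.
- **Section 5.2.1:** state that the 5% per comparison does not apply to this primary family. This sentence is needed for the Holm rule to take effect, and it also removes the conflict with 5.1.
- **Reporting:** if 98.3% intervals are given, label them as not matching the Holm decision.
- **Analysis plan:** carry the same rule into it before outcome data are examined.

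The cost is a few sentences in two documents, with no extra patients, visits or data. The price in inference is a higher error on a null scale when the others respond, within the overall 5%, and less simple intervals.

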### **Definition of study populations**

- Total population: All participants included.
- Eligible population: All participants included without major violation of eligibility criteria.
- Intention to treat population: All patients will be included in the analysis in the group in which they were initially randomised and all their data will be used.
- Per protocol population: Only patients who are strictly compliant with the procedure will be included (Lost-to-follow-up will be, in particular, excluded)

## **5.2. Hypotheses and number of participants needed**

### **5.2.1. Analysis strategy**

An intention-to-treat analysis with replacement of missing data by multiple imputation will be performed as the principal analysis. To check the robustness of the results of the ITT analysis, sensitivity analysis will be performed.

A per protocol analysis on available data could be carried out a second time.

Descriptive analysis will always be presented overall and per treatment group.

Comparative analysis between procedure groups will be systematically performed. All comparisons will be performed with a type I error of 5%.

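### Section 5.2.1 sets 5% for all comparisons, but the three primary scales were sized at 1.6% each; testing them at 5% gives about three times the family-wise error of the 1.6% design

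*Protocol*

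**What the plan says.** Section 3.1 of the protocol states that "Three scales of the QLQ-C30 questionnaire are considered as primary endpoints": global health status, physical functioning and emotional functioning, each at 6 months.

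Section 5.1 bases the sample size on detecting a difference "for at least one of the three targeted health-related quality of life (HRQoL) scores" and adds that "Each of the three scales will be independently tested". It gives the level and the result: "With a 1.6% two-sided type I error and a statistical power of 90%, the minimum number of patients to include is 222". Allowing for 20% dropout this becomes 278, and after the stepped-wedge adjustment 720.

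Section 5.2.1, which governs the analysis, makes multiply imputed intention-to-treat the principal analysis, calls for comparisons between groups, and closes with "All comparisons will be performed with a type I error of 5" per cent. It does not exempt the primary scales. Section 5.2.3 defers detail to a later statistical analysis plan. No other section says which level applies to the primary tests.

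**The concern.** With three primary tests and success on any one of them, the chance of at least one false positive exceeds the level of a single test. A per-scale level of 1.6%, close to 5%/3, is what one would choose to hold the overall error near 5%. Section 5.2.1, read literally, replaces that level with 5% on each scale and leaves the any-one-of-three rule without protection.

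The practical consequence is the trial's conclusion. A primary scale with p = 0.03 is significant under Section 5.2.1 and not significant at the level in Section 5.1. An analysis plan could adopt either level and cite the protocol for it. The methodology is written for both FRONE and TWOBE, so the ambiguity carries into two trials.

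**Working it through.** **Inputs (Sections 3.1 and 5.1).** Three primary scales; difference Δ = 10 points; SD σ = 20; power 90%; two-sided α = 0.016 per scale; dropout 20%; intra-cluster correlation 0.10; eight sites; 10 patients per site and step; equal arms (360 and 360). From Section 5.2.1: α = 0.05. The protocol gives no correlation between the scales, so a range is assumed below.

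**Step 1: which level produced 222?** The normal approximation is n per arm = 2σ²(z₁₋α/₂ + z₀.₉₀)²/Δ² = 8(z₁₋α/₂ + 1.2816)².

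| α (two-sided) | Normal approximation, per arm (total) | t-test, per arm (total) |
|---|---|---|
| 0.016 | 8 × (2.409 + 1.282)² = 109.0, so 109 (218) | 111 (222) |
| 0.05/3 | 109 (218) | 110 (220) |
| 0.05 | 8 × (1.960 + 1.282)² = 84.1, so 85 (170) | 86 (172) |

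The t-test calculation at 1.6% gives the stated 222 exactly. At 5% the total would be 170 to 172.

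**Step 2: does 720 rest on it?** Dropout: 222/(1 − 0.20) = 277.5, so 278, as stated. The usual stepped-wedge design effect, with one baseline period, eight single-site steps and 10 patients per cell, is

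[1 + 0.1 × (80 + 10 − 1)] / [1 + 0.1 × (40 + 10 − 1)] × 3 × 0.9 / [2 × (8 − 1/8)] = (9.9/5.9) × (2.7/15.75) = 0.288.

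Then 278 × 0.288 ≈ 80 per period, and 80 × 9 periods = 720. The stated total therefore starts from 1.6%. The protocol does not name its design-effect formula; this is a standard one that returns its figure.

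**Step 3: family-wise error under each level.** For three independent tests it is 1 − (1 − α)³:

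- α = 0.05: 1 − 0.95³ = 0.143 (upper bound 3 × 0.05 = 15%)
- α = 0.016: 1 − 0.984³ = 0.047 (upper bound 3 × 0.016 = 4.8%)

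Three scales of one questionnaire in the same patients will be correlated. Simulating three equally correlated normal statistics (4 million draws each) gives:

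| Assumed correlation | Each at 5% | Each at 1.6% | Ratio | 5% column against nominal 5% |
|---|---|---|---|---|
| 0 | 14.3% | 4.7% | 3.0 | 2.9 times |
| 0.3 | 13.6% | 4.6% | 3.0 | 2.7 times |
| 0.5 | 12.5% | 4.3% | 2.9 | 2.5 times |
| 0.7 | 10.9% | 3.8% | 2.9 | 2.2 times |
| 0.9 | 8.4% | 2.9% | 2.9 | 1.7 times |

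The ratio to the 1.6% design barely depends on the correlation. The excess over a nominal 5% does, but it is present at every value shown.

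**The case against.** The strongest reply is that the two sections can be read together: 5% is the overall level, 1.6% is its share per scale, and the specific statement about the primary scales governs the general one. That may well be what was intended. However, Section 5.2.1 speaks of every comparison, follows directly on the principal analysis and makes no exception, so the reader has to supply the reconciliation.

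Two parts of the argument are also inferred. The protocol never calls 1.6% a multiplicity correction, and the any-one-of-three criterion appears as a sizing target, not as a formal success rule. Both inferences are strong, because 1.6% has no other evident origin and each scale is to be tested separately, but they should be recognised as inferences. If 1.6% were only a planning figure, the protocol would contain no multiplicity control at all, which is no defence.

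It can also be said that this document is a summary of methodology and that a detailed analysis plan was due to follow. That plan is not available here, so it cannot be said that 5% will in fact be applied to the primary scales. But the complaint is not about missing detail: the protocol states two different levels for the same tests.

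Finally, the 14.3% assumes independent scales and is the upper end of the range shown. That stands, and is why the range is given.

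**Conclusion.** The concern holds. Sections 5.1 and 5.2.1 give different significance levels for the three primary tests, and the one in the analysis section does not match the sample size. With success on any one scale, testing each at 5% gives a family-wise error of 14.3% under independence, 12.5% at correlation 0.5 and 10.9% at 0.7, against 4.7%, 4.3% and 3.8% at 1.6%. That is about three times the error of the 1.6% design at any correlation from 0 to 0.9, and 1.7 to 2.9 times a nominal 5%. These figures rest on the any-one-of-three success rule and on assumed equal correlations. The contradiction itself rests on neither. Because it decides whether a trial is declared positive, it should be settled before any outcome data are seen.

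**What to change.** Replace the closing sentence of Section 5.2.1 with one that says three things: each of the three primary scales is tested two-sided at 1.6%; the trial is positive if at least one is significant at that level; and the 5% level applies only to the other comparisons. Section 5.1 should add that 1.6% is the per-scale share of an overall 5%, if that is confirmed as the intention. The analysis plan should carry the same wording.

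Holm's step-down procedure at a family-wise 5% is an acceptable alternative. It is never less powerful than Bonferroni, though it helps only with the second and third scales once the first is significant. If it is preferred, it should replace the fixed 1.6%, so that only one rule stands.

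The cost is a sentence or two of text. No patients are added, because 720 is already derived from 1.6%.

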### **5.2.2. Statistical method**

Qualitative variables will be described by numbers and percentage.

Quantitative variables will be described by numbers, mean, standard deviation, median, range, and interquartile range.

We will attempt as much as possible to associate a graphic representation of the analyses.

Statistical analyses will be performed with the SAS® software (version 9.4) and R software according on the type of analysis.

### **5.2.3. Analysis plan**

A detailed statistical analysis plan will be developed Q4 2022 and submitted as deliverable D4.10.

[www.geronteproject.eu](http://www.geronteproject.eu)

[[contact]](mailto:[contact])

This project has received funding from the European Union's Horizon 2020 research and innovation programme under grant agreement [945218](#). The sole responsibility for the content of this project lies with the authors. It does not necessarily reflect the opinion of the European Union. The European Commission is not responsible for any use that may be made of the information contained therein.
